2.5. Potential Risks and Benefits

2.5.1. Potential Risks

Effects of finger sticks and venous blood draws. Risks of bruising, bleeding, infection and fainting can accompany these procedures. Study-related blood collection for malaria diagnostic testing by rapid diagnostic test and for a dried blood spot sample can be accomplished by using finger stick or earlobe stick. Venous blood will only be obtained routinely from participants with RDT+ infections detected either in screening, enrollment, follow-up, or in active or passive surveillance.

DNA sequence information. Samples will be used for genotyping and/or sequencing malaria parasite RNA and/or DNA (nucleic acids). Left-over samples will be archived, with consent from study subjects, for future investigations—potentially including analysis of human nucleic acids or nucleic acids from other infectious organisms—with further appropriate approval. For example, future studies may investigate the presence of other causes of fever in participants with fever but negative malaria tests, or genomic studies of human migration to complement those of parasite migration.

Potential risks to study personnel. The main risks to study personnel are from accidental exposure to blood and body fluid borne infections. SOPs for staff safety are used in clinical and laboratory areas, including sharps management, hazardous waste management, etc. Universal precautions are used for handling all body fluids.

2.5.2. Known Potential Benefits

Participants may not receive any direct benefit from their participation in the study. However, if symptoms of malaria or other illnesses are noted, participants will be referred for prompt evaluation and treatment by the appropriate local health provider. By providing evidence-based strategies for malaria elimination, the information gained from the proposed work is beneficial for the study participants in the future, others living with malaria or in malaria-endemic regions, as well as public health professionals and policymakers in Myanmar and in the GMS, who are leading regional malaria elimination efforts.

3. OBJECTIVES AND OUTCOMES

Primary objective:

Make a preliminary assessment of the dynamics of subclinical malaria detected by ultrasensitive PCR to guide the design of a matched cohort study of subclinical malaria in Myanmar and along its borders with China and Bangladesh

(The objective of the subsequent matched cohort study, to be reviewed as a separate protocol, will be to compare the incidence of clinical malaria and malaria transmission capacity, in participants with and without subclinical malaria.)

Secondary and exploratory objectives:

1. Within usPCR+ and usPCR- cohorts, test for association between demographic and other risk factors (e.g. occupation, travel) and incidence of clinical malaria and transmission capacity
2. Collect preliminary data to estimate the history of exposure to malaria parasite and mosquito vector species by serological profiling
3. Collect preliminary data to develop a model system to predict future malaria risks using geospatial and satellite data on environmental conditions, patterns of parasite migration and human mobility, field data on vector abundance and malaria burden over time at study sites

Primary outcomes:

1. Proportion of individuals with initially positive usPCR tests that were followed by 1 or more consecutive positive tests on weekly or biweekly testing
2. Proportion of individuals with initially negative usPCR tests that subsequently had at least one usPCR positive test at a second screening 2-4 weeks later.

Primary endpoints:

Not applicable

Secondary and exploratory outcomes:

Infection outcomes and endpoints

1. Incidence of falciparum malaria infection by RDT
2. Incidence of vivax malaria infection by RDT
3. Incidence of mixed falciparum/vivax malaria infection by RDT
4. Incidence of falciparum malaria infection by usPCR
5. Incidence of vivax malaria infection by usPCR
6. Incidence of mixed falciparum/vivax malaria infection by usPCR

Serology endpoint

Seroreactivity to polymorphic malaria/mosquito proteins

4. STUDY DESIGN

4.1. Overview

- Prospective, multi-site short longitudinal study
- Up to six study sites, each with >2 villages, towns, unions, refugee camps or plantations, or a single military base. Alternative and additional sites may be added to ensure enough infected cases.
- Screening for eligibility (age at least 0.5 year; able & willing to strictly follow study protocol and to provide written informed consent or assent as appropriate)
- Enroll and consent eligible individuals
- RDT-positive: one-time enrollment for data and venous blood collection; Refer to and ensure appropriate treatment by care providing team; No study-related follow up
- RDT-negative: Collect data and DBS samples; Return to research clinic in 2-4 weeks
- PCR-negative participants: One follow up visit approximately 2-4 weeks after enrollment
- PCR-positive participants: Five follow up visits at approximately 4, 6, 8, 10, and 12 weeks (for those with total 12 weeks follow up) or 2, 3, 4, 5 and 6 weeks (for those with total 6 weeks follow up) after enrollment
- Total up to 6000 residents in up to six study site of all ages in villages, refugee camps, military bases, and work sites are to be enrolled
- Finger stick blood sampling will be done for RDT and dried blood spot sampling in all participants at each scheduled and unscheduled visit.
- Venous sampling will be done for participants with RDT+ infections detected at times when study staff trained for venous sampling are present. Blood volumes at any time point are limited to 2 mL for children aged < 3 years, 3 mL for age 3-5 years, and 5 mL for older children and adults.
- Estimated duration of study: 18 months

[†]All malaria. API data for some townships is reported only for all malaria (any positive RDT). Based on prevalence data, API for Kachin State site is likely to be mostly *P. vivax*. RDT, rapid diagnostic test for malaria; usPCR, ultrasensitive polymerase chain reaction; API, annual parasite index (cases per 1000 population at risk/year); NA, not available—range across villages not available for areas only reported by township.

asked to provide venous blood.

5. STUDY POPULATION

5.1. Selection of the Study Population

Sites broadly representative of the range of malaria epidemiologies seen in the region (Table 1, Figure 3) have been identified based on available data on the incidence of clinical malaria and prevalence of subclinical malaria (measured by both standard testing and by usPCR in surveys we have supported). In a staged fashion, initial screening will be undertaken at these sites, starting with the sites in Myanmar, where laboratories proficient in usPCR have been established.

To account for the possibility that malaria rates have declined since the latest available data were collected, alternative and additional sites may be identified in consultation with our research partners and local NMCP officials. The addition or substitution of additional sites will be reported to the study sponsor and IRBs.

Children will be included because they may be at risk for malaria, as well as to measure age-specific infection pattern which is expected to vary across sites. Adults of all ages—including pregnant women and the elderly—will be included to address the paucity of data on transmission potential in these groups and to detect chronic infections persisting even in the absence of recent exposure.

Because technical capacity for molecular diagnosis required for this study is not yet established at the Bangladesh and China sites, the study will begin at Myanmar sites following review and approval by the Myanmar and U.S.-based IRBs. As laboratory facilities are established in Bangladesh and China, the protocol will be reviewed by IRBs in those countries. Study activities in each country will only be started after review and approval by the IRB(s) in that country.

5.2. Sampling Strategy

The primary aim of the screening process is *not* to obtain an unbiased measurement of malaria prevalence, which is already known to be low in many sites. Rather, it is to identify and enroll in the study the target number of cases of subclinical malaria infection, which are expected to be rare. People and locations suspected or known to harbor malaria will be targeted for screening, based on: RDT and usPCR cross-sectional prevalence data from our ongoing

Figure 3. Study Sites and partners. Department of Medical Research:
(1) Ann Township, Rakhine State and (2) Madaya Township, Mandalay Region; Defence Services Medical Research Centre: (3) Monywa Township, Sagaing Region; National Institute of Parasitic Diseases, Chinese CDC: (4) Waingmaw Township, Kachin State/Nabang, Yingjiang County, China and (5) Mongmao Township, Shan State/Canguan County, Yunnan Province, China; icddr,b: Rajbila and Kuhalong Unions, Bandarban District, Bangladesh.

0 50 100 150 200 Miles

separately-funded malaria surveillance activities; RDT-based malaria incidence data from NMCPs and our own previous and ongoing research and surveillance activities; village clinic treatment logs; interviews with local health providers and community leaders; and results of initial screening.

As the screening process progresses, household and workplace contacts of RDT+ and usPCR+ cases will be traced to find more infected individuals until enrollment targets are reached. This targeted screening means that the overall sampling framework will be neither random nor fully representative of the larger communities. However, whenever possible, comprehensive or representative sampling will be done to provide unbiased prevalence estimates of *P. falciparum* and *P. vivax* infection for specific locations or populations within the larger study areas (e.g. sampling all individuals in a village).

While sampling strategies will necessarily be locale-specific (e.g. clinic-based, school-based, military-based or household-based), at each location the basis for sampling will be carefully documented so that we can ascertain when unbiased estimates of prevalence can be made for specific locations or populations. Each site has a central location for screening, enrollment and follow-up and satellite locations, e.g. clinics or schools, where study activities will occur.

5.3. Inclusion/Exclusion Criteria

5.3.1. Inclusion criteria for pilot study

Participants must meet all the inclusion criteria to participate in the study: 1) Age 6 months or older at the time of screening; 2) Written informed consent obtained (from the parent/guardian if the subject is less than 18 years old).

5.3.2. Exclusion criteria

Any condition which in the view of the investigator makes participation not in the best interests of the prospective participant. Any condition that would interfere with study participation or pose risks to participants. Those with clinical malaria infection as diagnosed by positive RDT may be invited to return and be re-screened for study eligibility after treatment and resolution of their illness.

6. STUDY PROCEDURES/EVALUATIONS

6.1. Study Procedures

6.1.1. Screening process

People and locations suspected or known to harbor malaria will be targeted for screening, as described above. As screening progresses, household and workplace contacts of RDT+ and usPCR+ cases will be traced to find more infected individuals until enrollment targets are reached. The sample collection schedule is shown in Table 2.

A very small number of individuals who are found to be RDT+ during the screening process will be asked to provide venous blood, dried blood spots, and travel history. Individuals who are found to be RDT+ during screening, or at any time during the study, will be referred promptly to local health providers for ACT treatment, in compliance with WHO recommendations and NMCP policies, which call for treatment of any RDT+ infection.

Table 2a. Study procedures for population with total 12 weeks of follow up

Procedures	Screening	Follow-up visits in weeks after enrollment				
		4	6	8	10	12
Eligibility/ RDT testing	R					
Informed consent/assent	R					
Enrollment	R					
Contact & demographic Information; hemoglobin testing	R					
Travel history	R	R	R	R	R	R
Dried blood spots (RDT- & usPCR+ at enrollment)	R	R	R	R	R	R
Dried blood spots (RDT- & usPCR- at enrollment)	R	R				
Venous blood collection for RDT+		R; Any time during the study				
Treatment referral for RDT+		S; Any time during the study				

RDT, rapid diagnostic test; usPCR, ultrasensitive PCR; R, research-related procedure; S, standard care procedure

Table 2b. Study procedures for population with total 6 weeks of follow up

Procedures	Screening	Follow-up visits in weeks after enrollment				
		2	3	4	5	6
Eligibility/ RDT testing	R					
Informed consent/assent	R					
Enrollment	R					
Contact & demographic Information; hemoglobin testing	R					
Travel history	R	R	R	R	R	R
Dried blood spots (RDT- & usPCR+ at enrollment)	R	R	R	R	R	R
Dried blood spots (RDT- & usPCR- at enrollment)	R	R				
Venous blood collection for RDT+		R; Any time during the study				
Treatment referral for RDT+		S; Any time during the study				

RDT, rapid diagnostic test; usPCR, ultrasensitive PCR; R, research-related procedure; S, standard care procedure

Eligible and consenting individuals will provide dried blood spot (DBS) samples, demographic and travel information, and contact information. DBS will be analyzed using usPCR methods in designated laboratories. Of those tested at the initial screening visit, usPCR- participants will return for just one additional follow up visit at approximately 4 weeks, at which time a second DBS and updated travel information will be collected. Individuals who test usPCR+ at the initial screening will also return approximately 2-4 weeks after the initial screen, and again for four additional visits (weeks ~6, 8, 10, and 12 or weeks ~2, 3, 4, 5 and 6), with DBS and travel history update collected at each visit.

6.1.2. Enrollment in preliminary study

Eligible and consenting individuals will be enrolled in the study. Eligibility criteria are listed in Section 5.3.

[figure not shown]
6.1.3. Follow-up

All enrolled participants will follow up 2-4 weeks after enrollment. Those who are found to be usPCR negative will provide one additional DBS at a second visit at 2-4 weeks and discharged from the study. Those who are found to be usPCR positive will provide four additional DBS, two weeks apart (weeks 6, 8, 10, and 12), and discharged from the study at Week 12. For the military population who are likely able to provide a total of only 6 weeks follow up, they will return at 2 weeks after enrollment, and the follow up schedule will be weekly.

At each follow up visit, a brief history (including travel history update) will be taken, and dried blood spots will be collected. Those who miss two consecutive follow-up visits will be

discharged from the study. At any time that participants are found to be RDT+, if study personnel qualified to collect venous blood are present, RDT+ participants will provide venous blood for serology and parasite nucleic acid sequencing. Individuals testing RDT+ at any time during the study will be referred for prompt ACT treatment of malaria by local health providers.

Conceptual framework of the study is shown below:

Anticipated duration of screening and enrollment phase: Screening and enrollment will begin at each site after obtaining ethical approval from all relevant administrative and ethical review committees for that site. Because technical capacity for usPCR is not yet established at the China and Bangladesh sites, the study is expected to begin sooner at the Myanmar sites. Screening will be continued until enrollment targets are reached.

Duration of follow-up for each subject: Up to 4 months (~2-4 weeks initial assessment plus up to 1.5-3 months follow-up).

Total study duration: Up to 1.5 years

Retention: We have achieved retention rates of >95% in longitudinal cohort studies in Madaya (unpublished) and Bandarban [54-58] by maintaining strong relationships with the community, including regular community meetings; contributing to community welfare through training health providers and upgrading facilities; and treating informed consent as an ongoing process for the individual and the community [59, 60]. Retention is expected to be lower at sites with refugees and military troops, requiring additional screening at those sites, as noted above.

Study termination: Participants will end their participation in the study when they miss two or more consecutive follow-up visits. Participants who return after more than two consecutive missed visits will be eligible to be re-screened and re-enrolled as a new participant.

Study visit schedule and primary evaluations: Active surveillance will consist of scheduled visits every 1-2 weeks for procedures shown in Table 2a and 2b. Passive surveillance will be conducted by encouraging participants to see the local health provider when ill. Local providers will collect dried blood spot samples whenever RDTs are done and will notify study staff of positive tests so that venous blood can be collected. In accord with WHO and NMCP policies in all three countries, any positive RDT result, whether testing was done as part of active or passive surveillance, will result in referral for ACT treatment, which will be administered by local providers as routine care and not as part of the study.

6.1.4. Sample Collection

Dried blood spots at all encounters. Our usPCR method preserves both DNA and RNA in 0.3 mL of blood collected in capillary tubes initially [22], and we have successfully adapted this method for DBS on filter paper, achieving nearly the same LoD. At sites and times when our dedicated study personnel are present to collect samples, DBS will be collected on two filter papers from finger-stick samples. When local health providers collect samples in the absence of research staff—e.g. when evaluating fever episodes during unscheduled visits, DBS will be collected, following standard procedures that we have successfully trained local health providers to perform at dozens of remote sites in Myanmar [22], Bangladesh [54] and China [9].

Whole blood during RDT+ malaria episodes. While DBS and no requirement for cold chain is field-friendly and simpler, the ability to sequence parasite genes is impaired by the low parasite density. In addition DNA degrades overtime without cold chain. As DNA quantity from DBS is not sufficient for whole genome sequencing, venous sampling will be done for RDT+ infections detected in screening, follow-up or active surveillance. Blood volumes at any time point are limited to 2 mL for children aged < 3 years, 3 mL for age 3-5 years, and 5 mL for children aged >5 years and adults. We have extensive experience recovering sera and cryopreserved parasites from small blood volumes collected from children [61-65] and have developed and used protocols for preserving RNA from field samples in Southeast Asia [22, 66].

Quality control and assurance. QC/QA procedures will be followed, including routine monitoring and evaluation of study records, using regularly updated study-specific and general standard operating procedures, and providing periodic refresher training in Good Clinical Practices.

6.2. Laboratory Evaluations

6.2.1. Laboratory evaluations/Assays

Dried blood spots (DBS) on filter paper will be used for usPCR assays and other targeted molecular genotyping and serological assays [45-47]. Venous blood samples will be used for serology, genotyping [67, 68], targeted and genome-wide sequencing [69-71], and related analyses.

To the greatest extent possible, laboratory analyses, including molecular assays and probing of microarrays, will be conducted at malaria research laboratories of collaborating institutions in the region (DMR, DSMRC, icddr,b and NIPD), in close collaboration and with technical support from the Duke University malaria team. A subset of samples will be shipped to Duke University malaria and collaborating genomic laboratories for advanced analyses such as whole genome sequencing and assembly [70-72] and for quality assurance procedures.

6.2.2. Specimen Collection, Preparation, Handling and Shipping

6.2.2.1. Instructions for Specimen Preparation, Handling, and Storage

Blood spots on two types of filter paper for study analyses will be collected at the time of blood collection for malaria diagnostic testing. DBS specimens will be collected using standard methods [73].

DBS and venous blood samples will be labeled with a participant ID and demographic information. After collection, blood spot samples will be air dried and stored in zip-lock plastic bags with desiccant at each site in a cool, dry, location.

Venous blood samples obtained from RDT+ participants will be collected into tubes with anticoagulant, frozen, and stored in either liquid nitrogen dry shippers or -20 °C or -80 °C freezers. Frozen samples (either blood or extracted DNA) may be shipped to the Duke University in dry ice containers or liquid nitrogen dry shippers.

Future studies of parasite DNA derived from samples may be conducted without restriction. Relevant studies of human RNA or DNA, such as human polymorphisms associated with risk of or protection from malaria, or genomic studies of human migration patterns, may be done on archived samples or nucleic acids only if specific permission for additional such studies is obtained from the relevant IRBs. Study participants will have the right to withdraw their permission for further use of their samples at any time during and after the study.

6.2.2.2. Specimen Shipment

Samples will be shipped periodically to the malaria laboratories at Duke University in Durham NC or other collaborating laboratories for specialized genotyping/probing that cannot be done in the region. Frozen venous blood samples will be sent in liquid nitrogen dry shippers or on dry ice to Duke University. Specimen receipt will be logged into an inventory database.

7. STATISTICAL CONSIDERATIONS

7.1. Study Outcome Measures

Primary objective:

Make a preliminary assessment of the dynamics of subclinical malaria detected by ultrasensitive PCR to guide study design of a subsequent longitudinal matched cohort study.

(The objective of the subsequent matched cohort study, to be reviewed as a separate protocol, will be to compare the incidence of clinical malaria and malaria transmission capacity, in participants with and without subclinical malaria.)

Secondary and exploratory objectives:

1. Measure the dynamics of subclinical malaria over time and obtain a preliminary estimate of the chronicity of infection over a short period of time
2. Test for association between demographic and other risk factors (e.g. occupation, travel) and incidence of clinical malaria and transmission capacity
3. Collect preliminary data to estimate the history of exposure to malaria parasite and mosquito vector species by serological profiling
4. Collect preliminary data develop a model system to predict future malaria risks using geospatial and satellite data on environmental conditions, patterns of parasite migration and human mobility, field data on vector abundance and malaria burden over time at study sites

Primary outcomes:

1. Proportion of individuals with initially positive usPCR tests that were followed by 1 or more consecutive positive tests on biweekly testing
2. Proportion of screened individuals with negative usPCR tests that subsequently had usPCR positive tests at a second screening test 4 weeks later

Primary endpoints:

Not applicable

Secondary and exploratory outcomes:Infection outcomes and endpoints

1. Incidence of falciparum malaria infection by RDT
2. Incidence of vivax malaria infection by RDT
3. Incidence of mixed falciparum/vivax malaria infection by RDT
4. Incidence of falciparum malaria infection by usPCR
5. Incidence of vivax malaria infection by usPCR

6. Incidence of mixed falciparum/vivax malaria infection by usPCR

Serology endpoint

Seroreactivity to polymorphic malaria/mosquito proteins

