2.2.2. Dynamics of Asymptomatic or Subclinical Malaria Identified by Ultrasensitive PCR

It is well known that many asymptomatic infections may persist for from weeks to months [31-33]. Persistent chronic cases of malaria infection in the absence of new exposure has been described [34]. A recent paper extensively reviewed the nature and dynamics of asymptomatic malaria and its clinical and transmission impact in different transmission zones [35]. However, most of these studies were conducted in areas of high malaria transmission, and used standard methods such as microscopy or RDTs LoDs far higher than that of usPCR. Studies that used sensitive molecular methods in low transmission regions [36, 37] are limited to cross-sectional surveys, and do not assess the dynamics or chronicity of these low-density infections. The natural dynamics of low density malaria infections in humans is unknown; although it has been suggested that these may be chronic infections, their duration has not been described.

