2.4.1. Preliminary study

In this study, a small number of asymptomatic infections detected by ultrasensitive PCR (usPCR) will be followed and tested intensively for three months to measure the temporal dynamics of these infections. A much larger number of uninfected individuals will be followed

for just 2-4 weeks (two visits), providing a comparator group for the infected cohort. The validity of our results in a subsequent matched cohort study depends, in part, on our ability to accurately classify infection status using a single usPCR result. In other words, do we have sufficient confidence in the correct classification of malaria infection positive and negative status using usPCR test at the beginning of the study? While there is no gold standard test more sensitive than usPCR, repeated usPCR testing offers a surrogate. Presumably, in a low transmission setting, someone who is truly uninfected on the first testing should remain negative on multiple consecutive tests, but this remains to be confirmed.

If this initial evaluation confirms that usPCR results are relatively stable - i.e., that most usPCR+ infections remain positive on most or all repeated testing over the course of three months, and that most usPCR- infections remain negative upon re-testing 2-4 weeks later, then we can move forward with the cohort study with confidence that our initial classification of exposure is a meaningful basis for assessing subsequent outcomes. If, however, a single usPCR result is found to be "unstable", we may need to consider testing at least twice before assigning infection status. Similarly, we may wish to increase the sample size if we determine that the sensitivity and specificity of a single usPCR test (compared to results of multiple testing) is high enough to proceed with single testing at screening and enrollment, but lower than ideal (e.g. sensitivity/specificity 50-75%).

2.4.2. Design of the subsequent matched cohort study (to be submitted for ethical review later as a separate protocol)

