To provide the rationale for this preliminary study, the design of the subsequent matched cohort study is described briefly here. The principle design will be a matched cohort study. This choice of study design is based on the knowledge of generally low prevalence of malaria in most of the proposed study sites. Although a standard cohort study would be appropriate in a high transmission setting, it would be difficult, if not impossible, to reach adequate sample size in our study sites with such low prevalence. A retrospective case control design is also unsuitable, since it will not be possible to measure the exposure of interest (prior subclinical malaria) at the time that the primary outcome (RDT+ infection) is detected. Therefore, a matched case-cohort design similar those we have previously done in Mali [53] offers a good alternative to study a rare exposure.

Matching is not typically used in cohort studies because it precludes testing for association between matched variables and outcomes of interest. However, in this situation, independent association between clinical protection and transmission risk needs to be understood. Because subclinical infection is itself likely to signify higher malaria exposure risk, comparing rates of RDT+ infections and transmission capability in unmatched infected and uninfected cohorts would likely show that clinical malaria and transmission capacity are more common in the infected cohort simply because their initial infection signals greater malaria exposure. Therefore, for the subsequent cohort study we will match infected participants (cases) to uninfected controls, to control for covariates known and suspected to be associated with malaria risk. With this design, we will still be able to test for association with matched variables and outcomes of interest within (but not between) infected and control cohorts.

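### Primary outcome 1 (one or more consecutive positives) does not, on its natural readings, measure the usPCR stability that Section 2.4.1 says the study is meant to judge

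*Combined protocol and SAP*

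**What the plan says.** Section 2.4.1 states the use of the result. One usPCR could classify people in the follow-on cohort if "most usPCR+ infections remain positive on most or all repeated testing over the course of three months" and "most usPCR- infections remain negative upon re-testing 2-4 weeks later". If a single result proves unstable, testing at least twice may be considered. A larger sample may be chosen if accuracy against repeated testing is adequate but "lower than ideal (e.g. sensitivity/specificity 50-75" per cent.

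Primary outcome 1 in Section 7.1 is "Proportion of individuals with initially positive usPCR tests that were followed by 1 or more consecutive positive tests on biweekly testing". Section 3 keeps the threshold but allows weekly as well as biweekly testing. Section 7.4 repeats the phrase without saying which visit counts or how a run is defined.

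Section 4.1 and Tables 2a and 2b give usPCR+ participants five follow-up tests, at weeks 4, 6, 8, 10 and 12, or at weeks 2 to 6 on the short schedule. usPCR- participants have one retest. Section 7.2 expects 250 usPCR+ in total and at least 75% usPCR- among enrollees.

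Two other elements bear on dynamics: secondary objective 1 in Section 7.1 (chronicity over a short period) and the Markov models in Section 7.4, which are specified with monthly time points.

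**The concern.** The rationale asks about most or all of the repeat tests over three months. The outcome has a threshold of one. Depending on the reading chosen, the same data could be reported as near-complete stability or as a coin toss, and nothing fixes the reading before results are seen.

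The result is meant to guide whether the next study tests once, tests at least twice, or enlarges its sample. Duration cannot be assumed from elsewhere to fill the gap: Section 2.2.2 says of these infections that "although it has been suggested that these may be chronic infections, their duration has not been described".

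The negative side matters because Section 2.4.2 says "we will match infected participants (cases) to uninfected controls". Infections hidden among usPCR- people would contaminate those controls, and a majority staying negative would not reveal them.

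**Working it through.** **The plan's own figures.** 0.75 × 1,000 = 750 usPCR- per site, as Section 7.2 states. Observations are 1 + 5 = 6 for usPCR+ and 1 + 1 = 2 for usPCR-, also as stated. No precision or power is given for either primary outcome, so there is nothing further to reproduce.

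**Positive side, persistent infection.** Let s be sensitivity, with five independent follow-up tests. The 50% and 75% values are the ends of Section 2.4.1's range; 90% is added for comparison.

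| Reading | Formula | s = 50% | s = 75% | s = 90% | Change, 50% to 75% |
|---|---|---|---|---|---|
| Any 1 of 5 | 1 − (1 − s)^5 | 96.9% | 99.9% | 100.0% | 3 points |
| Next test | s | 50% | 75% | 90% | 25 points |
| At least 3 of 5 | binomial tail | 50.0% | 89.6% | 99.1% | 40 points |
| All 5 | s^5 | 3.1% | 23.7% | 59.0% | 21 points |

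Any 1 of 5 passes one half once per-test positivity exceeds 1 − 0.5^(1/5) = 12.9%.

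**Positive side, infections that clear.** Take a perfect test and an assumed exponential residual duration with mean 8 weeks, on the 12-week schedule. Next-test and any-1-of-5 positivity are both exp(−4/8) = 60.7%. At least 3 of 5 requires infection to week 8: exp(−8/8) = 36.8%. All 5 is exp(−12/8) = 22.3%. So the next-test reading can suggest that most infections persist when most do not last to week 8.

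**If detectability varies between people.** Assume beta-distributed sensitivity with intraclass correlation (ICC) 0.3 and no clearance. Among initial positives, next-test positivity is s + 0.3(1 − s): 65% at s = 50% and 82.5% at s = 75%, a difference of 17.5 points. At least 3 of 5 gives 70% and 89%, a difference of 19 points. Most of its advantage in separating sensitivities goes.

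**Stability is not sensitivity.** On the 12-week schedule, at least 3 of 5 is 50% at s = 0.50 with no clearance, 52% at s = 0.75 with an assumed 12-week half-life, and 47% at s = 0.90 with an assumed 8-week half-life. The schedules also differ: s = 0.75 with a 12-week half-life gives 52% on visits to week 12 and 68% on visits to week 6. The number of tests matters too: at s = 0.5, at least 3 of 4 is 31%, against 50% for at least 3 of 5.

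**Precision.** For 125 of 250 the exact 95% interval is 44% to 56%. With an assumed design effect of 2 it is 41% to 59%. Some clustering is likely, because Section 5.2 traces household and workplace contacts.

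**Negative side.** Let q be the share positive at screening. Assume perfect specificity, no new infection or clearance, and independent tests. True prevalence is q/s, the infected share of usPCR- is h = q(1 − s)/(s(1 − q)), and conversion is c = s × h = q(1 − s)/(1 − q). Since q/s cannot exceed 1, s is at least q, so c is at most q and the share staying negative is at least 1 − q. Section 7.2 implies q of 25% or less, hence at least 75% stay negative.

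- q = 25%, s = 50%: h = 33%, c = 16.7%, and 83% stay negative.
- q = 4% (Table 1, Madaya: 0.5 + 3.5, ignoring mixed infections), s = 50%: h = 4.2%, c = 2.1%, and 98% stay negative.

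New infections also raise c. With s = 0.9 and an assumed 1% newly infected, c = s × h + s × 0.01 × (1 − h). The estimate c/0.9 then reads 1.5% instead of the true 0.5% at q = 4%, and 4.7% instead of 3.7% at q = 25%.

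**The case against.** Section 2.4.1 is design rationale in tentative language, the study is described as largely descriptive, and Sections 3 and 7.1 state that primary endpoints do not apply. That stands: a reader might infer that the study fails a binding go/no-go rule, but the documents set no such rule and no pass mark. Section 2.4.1 is nevertheless the stated use of the result.

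A reader might also infer that no reading of the outcome could work. That goes too far. If runs of 1, 2 and up to 5 consecutive positives were tabulated, the run of five would recover the all-tests part of the criterion. The text, however, names one proportion with a threshold of one.

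Nor is it right that the plan otherwise ignores dynamics. The chronicity objective and the Markov models both address them, and the models are expressly meant to explain usPCR positivity over time. What is missing is a link from either to the Section 2.4.1 question. The monthly step also matches neither the weekly nor the biweekly visits.

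A further fair objection is that at least 3 of 5 is not a clean measure of sensitivity. It can also be met by positives at weeks 4, 6 and 8 alone. Both are true, so the cut-off should be the sponsor's to fix in advance.

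On the negative side, outcome 2 already yields the proportion needed. The 33% hidden-infection case sits at the ceiling of q, whereas Section 2.4.2 describes "generally low prevalence of malaria in most of the proposed study sites".

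**Conclusion.** The point holds as a mismatch of definition that should be fixed. On its two natural readings, primary outcome 1 does not measure the stability described in Section 2.4.1. Any 1 of 5 barely moves across the plan's own 50% to 75% range, and the next test cannot speak to three months. The mismatch itself rests on the text alone. The 97 / 50 / 50 / 3% spread rests on persistent infection and independent, equally detectable tests.

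It would be tempting to present at least 3 of 5 as much the better discriminator of sensitivity. The calculations support that only when detectability is similar across people (40 against 25 points). At an assumed ICC of 0.3 the gap is 19 against 17.5. The reason to prefer it is that it matches the question asked.

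The negative-side point is smaller and concerns interpretation. The 1 − q floor depends on perfect specificity and no new infections. It does not show that outcome 2 is defective or that a large share of controls would be infected at low-prevalence sites. The half-lives, mean duration, ICC, design effect and incidence are assumptions, not protocol figures.

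**What to change.** In Sections 3, 7.1 and 7.4, define primary outcome 1 as the proportion of initially usPCR+ participants who are positive on more than half of the follow-up tests taken before any treatment for an RDT+ result. That is at least 3 of 5 when follow-up is complete; another cut-off may be used if fixed beforehand. Report it:

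- with the full 0 to 5 distribution and positivity at each visit;
- separately for the 6- and 12-week schedules, and by number of tests taken;
- with 95% confidence intervals that allow for clustering.

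State that it measures stability of usPCR status, which mixes sensitivity with clearance; that only the 12-week schedule addresses three months; and that its advantage over next-test positivity in separating sensitivities depends on similar detectability across people. Match the Markov time step to the actual visit intervals.

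For the negatives, keep outcome 2. In Section 2.4.1, stop treating a majority staying negative as evidence of correct classification. Report conversion c by site beside that site's q, with the implied infected share of usPCR-, c/s, over a range of assumed s. Note that new infections and false positives also raise c.

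The cost is wording in four sections and a little more analysis, with no new samples or visits. The headline stability figure will be less favourable than any 1 of 5 would give.
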